5.9.2 Secondary outcome measures of tumor targeting

The tumor targeting potential will be visually scored as positive (intense, moderate or low) or negative by the PI.

We expect that patients with measurable HER2+ cancer lesions (lesions above 3cm) will be detectable using SPECT/CT. The activity per unit of volume will be quantified by the PI.

5.10 Adverse events / serious adverse events

5.10.1 Definitions

The definitions of the AEs and related terminology are those in the ICH E6 guidance. Grading will be evaluated according to CTCAE v4.0. AE coding will be performed with the MedDRA dictionary v18.1.

5.10.2 Documentation and reporting

All observed or volunteered AEs regardless of suspected causal relationship to the IMP will be recorded on the AE page(s) of the case report form. The investigator must assess all AEs for seriousness, severity and relation to IMP.

The investigator will follow all AEs, regardless of seriousness or severity, until the event or its sequelae resolve or stabilize at a level acceptable to the investigator.

The investigator is responsible for ensuring appropriate clinical management of all AEs until they are resolved or stabilized at a level acceptable to the investigator. Appropriate clinical management of AEs is at the discretion of the investigator.

All clinically significant abnormal laboratory tests occurring during the study will be repeated at appropriate intervals until they return to baseline or to a level deemed acceptable by the investigator, or until the abnormality is explained by an appropriate diagnosis.

5.10.3 Expedited reporting of serious adverse events (SAEs)

Any SAE must be reported to the sponsor within 24h of awareness. Such events will be documented in the best possible detail on the SAE Report Form to be transmitted to the sponsor by fax or email. The immediate report shall be followed by detailed, written reports. The immediate and follow-up reports shall identify subjects by unique code numbers assigned to the latter. AEs and/or laboratory abnormalities identified in the protocol as critical to safety evaluations shall be reported to the sponsor.

The contact information is as follows:

Sponsor's QPPV: [name] Semaphar sprl [name] Belgium [contact] E-mail: [contact]

Emergency 24-hour Contact: [name], PhD Camel-IDS NV [contact] [contact] E-mail: [contact]

For all these SAEs, the investigator is obligated to pursue and provide information as requested by the Sponsor or its designated representative in addition to that on the CRF. In general, this will include a description of the AE in sufficient detail to allow for a complete medical assessment of the case and independent determination of possible causality. Information on

CAMEL-IDS NV [name] www.camel-ids.com

other possible causes of the event, including concomitant medications and illnesses must be provided. The investigator's assessment of causality must also be provided. If causality is unknown and the investigator does not know whether or not study drug caused the event, then it should be attributed to the study drug.

In the case of a subject death, a summary of available autopsy findings must be submitted as soon as possible to the Sponsor or its designated representative. For reported deaths of a subject, the investigator shall supply the sponsor, the Ethics Committee and regulatory authorities with any additional information requested.

The sponsor shall keep detailed records of all AEs that are reported to him by the investigator or sub-investigators.

5.11 Statistical methods planned

5.11.1 Sample size justification

No statistical hypothesis has to be tested. Therefore, no formal sample size calculations have been made. The sample size has been determined based on literature (12).

Overall, 10 humans (healthy volunteers and patients pooled together) are going to be exposed to the IMP. For a sample size of 10, the probability of observing at least one event will be 90% (power) when the actual probability of the event is 20.6%, and a power of 80% will be ensured for an actual probability of the event of 14.9%. The probability (power) of observing an event having a frequency of 10% will be 65.1% and that of observing an event having a frequency of 5% will be 40.1%.

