5.4 Selection and withdrawal of subjects

5.4.1 Part I (Healthy volunteers)

Inclusion Criteria:

CAMEL-IDS NVBurgemeester EtienneDemunterlaan, 11090 Brusselswww.camel-ids.com

Subjects will only be included in the study if they meet all of the following criteria:

- Subjects who have given informed consent
- Subjects that agree not to drink alcoholic beverages or use any drugs during the study
- Subject with blood parameters within normal ranges
- Age: at least 18 years old

Exclusion Criteria:

Subjects will not be included in the study if one of the following criteria applies:

- Pregnant subjects
- Breast feeding subjects
- Subjects with occupational exposure to ionizing irradiation
- Subjects with clinical significant disease or on concomitant therapy (except contraception)
- Subjects with previous thyroid disorders
- Subjects that received radiolabeled compounds with a long half-life (>7h) for diagnostic or therapeutic purposes within the last 2 days.
- Subjects with absolute contra-indications for thyroid blockage with potassium iodide.
- Subjects with abnormal liver: ALT/AST > 2 times normal values; bilirubin > 1.5 time normal values.
- Subjects with abnormal kidney function: $< 50 \text{ ml/min}/1,73 \text{ m}^2$
- Subjects with recent (< 1 week) gastrointestinal disorders (CTCAE v4.0 grade 3 or 4) with diarrhea as major symptom
- Subjects with any serious active infection
- Subjects who have any other life-threatening illness or organ system dysfunction, which in the opinion of the investigator would either compromise subject safety or interfere with the evaluation of the safety of the test radiopharmaceutical
- Subjects who cannot communicate reliably with the investigator
- Subjects who are unlikely to cooperate with the requirements of the study
- Subjects at increased risk of death from a pre-existing concurrent illness
- Subjects who participated already in this study
- Subjects who participated in a previous trial with Anti-HER2 VHH1

Withdrawal of subjects

The subject may withdraw from the study at any time without giving reasons and without any disadvantageous consequences for his/her subsequent medical care.

The investigator may withdraw a subject from the study at any time in case of intercurrent illness, AE, therapeutic procedure or as a general rule if further participation in the study is believed to be to the subject's detriment.

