Any subject withdrawn from the study before the scheduled completion of the study procedures will be considered an early withdrawal, regardless of the reason for withdrawal. For safety

reasons, reasonable attempt should be made to contact withdrawn subjects 24h after the administration of the investigational product to gather information on AEs. For his/her own safety, subjects will be reminded to continue potassium iodide ingestion until 48±12h after administration of [¹³¹I]-SGMIB Anti-HER2 VHH1. Information collected as a result should be recorded on the appropriate case report form (CRF) pages. Subjects withdrawn from the study will be replaced.

Subject recruitment

Healthy subjects will be recruited by the PI using advertising approved by the ethics committee.

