5.4.2 Part II (Patients with HER2+ breast cancer)

Inclusion Criteria:

Patients will only be included in the study if they meet all of the following criteria:

- Patients who have given informed consent
- Patients that agree not to drink alcoholic beverages or use any drugs during the study
- Age: at least 18 years old
- Patients with local, locally advanced or metastatic HER2+ breast carcinoma as diagnosed on biopsied tissue by immunohistochemistry or fluorescence in situ hybridization (FISH).

Exclusion Criteria

Patients will not be included in the study if one of the following criteria applies:

- Pregnant patients
- Breast feeding patients
- Patients with occupational exposure to ionizing irradiation
- Patients with active thyroid dysfunction (abnormal TSH value)
- Patients that received radiolabeled compounds with a long half-life (>7h) for diagnostic or therapeutic purposes within the last 2 days.
- Patients with absolute contra-indications for thyroid blockage with potassium iodide.
- Patients with abnormal liver: ALT/AST > 2 times normal values; bilirubin > 1.5 time normal values.
- Patients with abnormal kidney function: < 50 ml/min/1,73 m²
- Patients with recent (< 1 week) gastrointestinal disorders (CTCAE v4.0 grade 3 or 4) with diarrhea as major symptom
- Patients with any serious active infection
- Patients who have any other life-threatening illness or organ system dysfunction, which in the opinion of the investigator would either compromise patient safety or interfere with the evaluation of the safety of the test radiopharmaceutical
- Patients who cannot communicate reliably with the investigator

CAMEL-IDS NV [name]	Page 18 of 36
www.camel-ids.com	

- Patients who are unlikely to cooperate with the requirements of the study
- Patients at increased risk of death from a pre-existing concurrent illness
- Patients who participated already in this study
- Patients who participated in a previous trial with Anti-HER2 VHH1

Withdrawal of patients

The patient may withdraw from the study at any time without giving reasons and without any disadvantageous consequences for his/her subsequent medical care.

The investigator may withdraw a patient from the study at any time in case of intercurrent illness, AE, therapeutic procedure or as a general rule if further participation in the study is believed to be to the patient's detriment.

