Any patient withdrawn from the study before the scheduled completion of the study procedures will be considered an early withdrawal, regardless of the reason for withdrawal. For safety reasons, reasonable attempt should be made to contact withdrawn subjects 24h after the administration of the investigational product to gather information on AEs. For his/her own safety, subjects will be reminded to continue potassium iodide ingestion until $48\pm12h$ after administration of [¹³¹I]-SGMIB Anti-HER2 VHH1. Information collected as a result should be recorded on the appropriate CRF pages.

Patients withdrawn from the study will be replaced.

Patient recruitment

Patients with HER2+ breast cancer will be recruited by the PI at UZ Brussel and possibly via the ClinicoBru patient recruitment network.

5.5 Clinical Laboratories, Technical Department(s), Institution(s) Providing Clinical Study Services

The local department of clinical chemistry and hematology will perform the clinical laboratory testing of blood samples.

The local nuclear medicine department will provide the analyses of the blood and urine samples:

Whole blood and plasma samples will be counted against appropriate standards of known dilution in an automatic gamma well counter and, after correction for decay and background activity, expressed as a percentage of the injected activity (%IA). The blood volume of each volunteer will be estimated according to body weight and height, using Nadler's formula and the subject's hematocrit

Plasma and urine aliquots will be analyzed by size-exclusion chromatography (SEC) or reverse-

phase high pressure liquid chromatography (RP-HPLC) to identify possible metabolites.

The PI of the local nuclear medicine department will also perform the analyses of the dynamic planar scan, the total body scans and the SPECT/CT scans.

From the dynamic planar scan, time activity curves for kidney and liver activity will be drawn. The total body scans will be used for region of interest analysis to derive input data for the OLINDA/EXM software 1.0 in order to calculate dosimetry data (12).

SPECT/CT scans will be analyzed visually and tumor uptake will be scored by the PI: intense, moderate, low or no uptake. In addition, tumor lesions will be quantified to obtain a measurement of activity per unit of volume.

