5.11.2 Safety

Safety of the [¹³¹I]-SGMIB Anti-HER2 VHH1 will be evaluated based on the adverse effects, their intensity and relationship to the investigational product. The evaluation is of a qualitative manner and no statistical inferential methods are planned for this objective. Classical descriptive statistics for categorical variables (N, n and %) will be used.

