5.12 Criteria for termination of the study

In case a SAE related to the IMP occurs, the trial will be stopped.

When the number of subjects that achieved the trial is equal to 6 healthy volunteers, the DSMB will evaluate the safety profile of the product and take the decision to include the 4 HER2+ breast cancer patients.

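### Does replacing withdrawn subjects leave it open whether a subject who was dosed and then withdrawn counts in the safety analysis?

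*Combined protocol and SAP*

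**What the plan says.** Section 5.11.1 (Sample size justification) states: "Overall, 10 humans (healthy volunteers and patients pooled together) are going to be exposed to the IMP". From n = 10 it gives the probability of seeing at least one event: 90%, 80%, 65.1% and 40.1% for true event rates of 20.6%, 14.9%, 10% and 5%. No hypothesis is tested.

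Section 5.4.1 (Part I) provides that "The investigator may withdraw a subject from the study at any time in case of intercurrent illness, AE, therapeutic procedure". It foresees withdrawal after dosing, since "reasonable attempt should be made to contact withdrawn subjects 24h after the administration of the investigational product to gather information on AEs", and directs that what is learned be entered in the case report form. It then says: "Subjects withdrawn from the study will be replaced". Section 5.4.2 (Part II) matches it: "The investigator may withdraw a patient from the study at any time in case of intercurrent illness, AE, therapeutic procedure", and "Patients withdrawn from the study will be replaced".

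Section 5.11.2 (Safety) describes a qualitative evaluation without inference: "Classical descriptive statistics for categorical variables (N, n and %) will be used". It does not say who makes up N.

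Section 5.12 sets the Data Safety Monitoring Board (DSMB) review: "When the number of subjects that achieved the trial is equal to 6 healthy volunteers, the DSMB will evaluate the safety profile". Section 5.2 leaves the DSMB's procedures to a charter that is not among the documents.

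**The concern.** Once a subject is dosed, withdrawn and replaced, those exposed and those who complete are no longer the same people. Section 5.11.1 gives one number for both, section 5.11.2 names no safety set, and section 5.12 times the DSMB review by a count that reads as completers.

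Safety is a primary objective in both parts, and an AE is a listed reason for withdrawal. If N meant completers, a subject removed because of an AE would leave both numerator and denominator, which would lower the reported incidence and could affect the decision to open Part II. The stopping rule in section 5.12 would not catch this, because it applies only to a serious adverse event (SAE) related to the product.

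**Working it through.** **1. The plan's own figures.** Inputs from section 5.11.1: n = 10 and the four event rates. Formula: P(at least one event) = 1 − (1 − p)^n.

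- p = 0.206: 1 − 0.794^10 = 0.900 (plan 90%)
- p = 0.149: 1 − 0.851^10 = 0.801 (plan 80%)
- p = 0.10: 1 − 0.90^10 = 0.651 (plan 65.1%)
- p = 0.05: 1 − 0.95^10 = 0.401 (plan 40.1%)

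All four reproduce.

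**2. Effect of replacement on these figures.** If k dosed subjects are replaced and the trial runs to ten completers, the number exposed is 10 + k.

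| Exposed | 10% event | 5% event |
|---|---|---|
| 10 | 65.1% | 40.1% |
| 11 | 68.6% | 43.1% |
| 12 | 71.8% | 46.0% |

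With all dosed subjects counted, replacement raises the probabilities slightly.

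**3. What the choice of count could do.** Suppose the withdrawn subject has the only AE.

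| Setting | Completers | All dosed |
|---|---|---|
| Part I, one replaced | 0/6 = 0% | 1/7 = 14.3% |
| Part II, one replaced | 0/4 = 0% | 1/5 = 20.0% |
| Whole trial, one replaced | 0/10 = 0% | 1/11 = 9.1% |

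The direction depends on who has the event. If the withdrawn subject has none and one completer does, completers give 1/10 = 10.0% and all dosed 1/11 = 9.1%.

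**4. Which count the text supports.**

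- Section 5.9.1, the primary safety outcome, requires both collection and evaluation of all AEs that subjects have.
- Sections 5.4.1 and 5.4.2 seek AE information from withdrawn subjects, for safety, and put it on the case report form.
- Section 5.10.2 records every AE, whatever its suspected cause.
- Section 5.11.1 bases its probabilities on people exposed to the product.
- No section restricts the safety evaluation to completers.

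These point to the right-hand column of the table in step 3.

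**5. The DSMB review.** The count of six in section 5.12 fixes when the DSMB meets. What it reviews is the safety profile of the product, which is wider than the experience of six completers. Without the charter, it cannot be shown that replaced volunteers' data are left out.

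**6. How often the question would arise.** The documents give no withdrawal rate. Assume a chance w per subject of withdrawal for an AE after dosing. The chance of at least one before m subjects complete is 1 − (1 − w)^m, and the expected number exposed is 10/(1 − w).

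| w (assumed) | Before 6 complete | Before 10 complete | Expected exposed |
|---|---|---|---|
| 2% | 11.4% | 18.3% | 10.2 |
| 5% | 26.5% | 40.1% | 10.5 |
| 10% | 46.9% | 65.1% | 11.1 |

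The documents suggest the low end. Section 5.2 allows one injection, so there is no later dose to discontinue. Scheduled procedures end at about 72 h in Part I and 24 h in Part II (section 5.3). Section 2 reports no related AEs in 20 patients given the same VHH with a different label.

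**7. Would calling ten a minimum improve section 5.11.1?** No. A related SAE stops the trial, and Part II opens only on the DSMB's decision (sections 5.2 and 5.12), so exposure can end at six or fewer. At n = 6 the detection probabilities are 1 − 0.90^6 = 46.9% and 1 − 0.95^6 = 26.5%, below the stated 65.1% and 40.1%. Ten is an ordinary planned number and is best left as one.

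**The case for a change.** The best case for a change is that no sentence settles the denominator. Section 3 words the primary objectives as safety in 6 volunteers and in 4 patients, so a programmer could set N to 6 and 4. Sections 5.9.1 and 5.10.2 govern collection more plainly than tabulation, and section 5.9.1 speaks of AEs during the study, which might be read to exclude an event learned of after withdrawal. A definition would cost a sentence and need no new data.

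Part of this stands: the safety set is unnamed, and the number exposed can differ from ten. The rest is weaker. The objectives give planned numbers and do not define an analysis set. Section 5.9.1 requires evaluation as well as collection. The 24-hour contact exists to gather AEs after withdrawal and sends them to the case report form, so they are study data. Reporting a dosed subject's AE while leaving that subject out of N would contradict the exposure basis of section 5.11.1. A defining sentence would record the reading the plan already supports and would alter no result.

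**Conclusion.** No change is needed. The plan leaves a term undefined that an analyst would fill in sensibly: AE percentages are taken over everyone who received the product, including those later replaced. On that reading the primary safety result is not biased, and the four probabilities are right for the planned ten and slightly conservative if a dosed subject is replaced and the trial runs to completion.

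The largest single-withdrawal contrasts, 0/6 against 1/7, 0/4 against 1/5 and 0/10 against 1/11, require a completers-only count that no section prescribes. Even then, in a qualitative evaluation of about ten people with every AE recorded, the event would be visible whatever the denominator.

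This rests on the supplied text. The DSMB charter and some removed pages were not available, so nothing is concluded about which data the DSMB receives. The withdrawal rates in the working are assumptions.

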5.11.2 Safety

Safety of the [¹³¹I]-SGMIB Anti-HER2 VHH1 will be evaluated based on the adverse effects, their intensity and relationship to the investigational product. The evaluation is of a qualitative manner and no statistical inferential methods are planned for this objective. Classical descriptive statistics for categorical variables (N, n and %) will be used.

5.11.3 Biodistribution and dosimetry

For the biodistribution evaluation, all organs with an uptake higher than the background (surrounding soft tissues) will be included in the evaluation as source organs.

The percentage of injected activity (%IA) will be calculated, in each set of images, as the ratio between the measured activity in the organ and the injected activity. Organ time activity curves

will be generated, plotting %IA vs. time. The individual and mean blood and plasma timeactivity curves will be obtained using the measured activity in blood and plasma samples.

All dosimetric evaluations will be done using the OLINDA/EXM 1.0 software (12). Total dose estimates and the dose estimate for the organs with the highest dose (most likely kidney and bladder) will be reported using classical descriptive statistics for continuous variables (N, n, mean, median, standard deviation, minimum and maximum).

5.11.4 Tumor uptake

Tumor uptake will be scored visually as positive or negative in all known tumor lesions. Classical descriptive statistics for categorical variables (N, n and %) will be used to characterize this variable.

5.12 Criteria for termination of the study

In case a SAE related to the IMP occurs, the trial will be stopped.

When the number of subjects that achieved the trial is equal to 6 healthy volunteers, the DSMB will evaluate the safety profile of the product and take the decision to include the 4 HER2+ breast cancer patients.

5.13 Overview of investigational actions

Table 1. Overview of the investigational actions that need to be performed at different visit times for each subject in part I of the study. V1: Visit 1; V2: Visit 2; V3: Visit 3; V4: Visit 4; V5: Visit 5

		V1	V2		V3					V4		V5								
Action	Total			pre	0min	5min	10min	20min	30min	40min	60min	105min	120min	225min	240min	4.5h	23.75h	24h	71.75h	72h
Informed consent	1	х																		
Inclusion/exclusion criteria	1	x																		
Medical history	1	х																		
Subject information: fasting&thyroid blocking drugs	2	х	х																	
Delivery thyroid blocking drugs	4		х	х													2x			
Confirmation of ingestion thyroid blocking drugs	4		х	х													х		х	
Blood sample for HCG test	1		х																	
Physical exam	2			х												х				
Vital signs	3			х		x										х				
Blood sample lithium heparine	13		х	2x		х	х	х	х		х	х		х			2x		х	
Blood sample EDTA	3		х	х													х			
Urine sampling	4										х			х			х		х	
Intravenous line&saline infusion	1			х																
Administration [¹³¹ I]-Anti-HER2 VHH1	1				х															
Measurement of residual activity in syringe and line	1				х															
If subject cannot withhold: urine collection&scan TB1	1									х										
Dynamic renal scan (30 min)	1				х															
Total body (TB) planar scan	5									х			х		х			х		x
Counting blood/plasma (radioactivity)	10			х		х	х	х	х		х	х		х			х		х	
HPLC analysis (metabolites in blood)	5						х				х			х			х		х	
HPLC analysis (metabolites in urine)	4										х			х			х		х	
Clinical chemistry/Hematology analysis	3		х	х													х			
HCG test	1		х																	
Dosimetry analysis Total body planar scans	5									х			х		х			х		х

CAMEL-IDS NV [name]	Page 29 of 36
www.camel-ids.com	

Table 2. Overview of the investigational actions that need to be performed at different visit times for each patient in part II of the study. V1: Visit 1; V2: Visit 2; V3: Visit 3; V4: Visit 4

		V1	/1 V2 V3								V4				
Action	Total			pre	0min	5min	15min	60min	120min	2.5h	3h	23.75h	24h	24.5h	
Informed consent	1	х													
Inclusion/exclusion criteria	1	х													
Medical history	1	х													
Patient information: fasting& thyroid blocking drugs	2	х	x												
Delivery thyroid blocking drugs	4		x	x								2x			
Confirmation of ingestion thyroid blocking drugs	3		x	x								x			
Blood sample for HCG test	1		x												
Physical exam	2			x							х				
Vital signs	3			x		х					х				
Blood sample lithium heparine	4		x	x				х				х			
Blood sample EDTA	3		x	x								х			
Intravenous line&saline infusion	1			x											
Administration [¹³¹ I]-Anti-HER2 VHH1	1				х										
Measurement of residual activity in syringe and line	1				х										
If patient cannot withhold: urine collection&scan TB1	1								х						
Total body (TB) planar scan	3						х		х				х		
SPECT/CT scan	2									х				х	
Counting blood/plasma (radioactivity)	1							х							
HPLC analysis (metabolites in blood)	1							х							
Clinical chemistry/Hematology analysis	3		x	x								х			
HCG test	1		х												

CAMEL-IDS NV [name]	Page 30 of 36
www.camel-ids.com	

DATA HANDLING AND RECORD KEEPING

